6.3 DOSE MODIFICATIONS AND DELAYS FOR IBRUTINIB AND GA101 – OBINUTUZUMAB

6.3.1 Dose Hold, Reduction, or Discontinuation of Ibrutinib

Treatment with Ibrutinib should be held for any unmanageable, potentially study drug-related toxicity that is Grade 3 or higher in severity. Subjects who require anticoagulant treatment (eg, heparin and/or warfarin) should have study drug hold until stable on anticoagulant therapy.

Ibrutinib may be held for a maximum of 28 consecutive days of toxicity. Ibrutinib should be discontinued in the event of a toxicity > Grade 1 lasting > 28 days.

A hematologic AE grading scheme for hematologic toxicity is included in Appendix 3.

The actions in Table 4 should be taken for the following toxicities:

- Grade 4 ANC (< 500/μL) for > 7 days (Neutrophil growth factors are permitted per ASCO guidelines) (Smith et al., 2006) and use must be recorded in CRF.
- Grade 3 or 4 platelets (< 50,000/µL); or, in subjects with baseline thrombocytopenia, a platelet decrease of 50-74% from baseline in presence of bleeding.

Ibrutinib + GA101 - Obinutuzumab. University of California, San Diego

- Grade 4 Platelets (< 25,000/μL); or, in subjects with baseline thrombocytopenia, decrease of > 75% from baseline or < 20,000/μL, whichever is higher.
 - Grade 3 or 4 nausea, vomiting, or diarrhea, if persistent despite optimal antiemetic and/or anti-diarrheal therapy, or any other Grade 4 toxicity and any unmanageable Grade 3 toxicity.

Table 4 Dose modifications or discontinuation actions for Ibrutinib

Occurrence ≥ G3	Action	
AE		
1 st	Hold Ibrutinib until recovery to Grade ≤ 1 or baseline; may restart	
	at original dose level	
2 nd	Hold Ibrutinib until recovery to Grade ≤ 1 or baseline; restart at	
	one dose level lower (280 mg daily)	
3 rd	Hold Ibrutinib until recovery to Grade ≤ 1 or baseline; restart at	
	one dose level lower (140 mg daily)	
4 th	Discontinue Ibrutinib	

6.3.2 Dose Modifications for Ibrutinib for Hepatic Impaired Subject

Ibrutinib is metabolized in the liver and therefore subjects with clinically significant hepatic impairment at the time of screening (Child- Pugh class B or C) are excluded from study participation.

Subjects while on study who develop significant clinical and/or laboratory signs and/or symptoms of liver dysfunction (e.g., transaminitis, jaundice, etc.) in the opinion of the investigator, should be assessed with the Child-Pugh Score (Table 5) to determine a dose reduction of Ibrutinib as described in Table 6:

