Table 5 Child-Pugh Score

The score employs five clinical measures of liver disease. Each measure is scored 1–3, with 3 indicating most severe derangement.

Clinical and Laboratory Criteria	1 Point	2 Points	3 Points
Hepatic	None	Mild to moderate	Severe
encephalopathy		(grade 1 or 2)	(grade 3 or 4)
Ascites	None	Mild to moderate	Severe
		(diuretic	(diuretic
		responsive)	refractory)

Ibrutinib + GA101 – Obinutuzumab. University of California, San Diego

Total bilirubin	<2	2 - 3	>3
(mg/dL)			
Seum albumin	>3.5	2.8 - 3.5	<2.8
(gr/dL)			
International	<1.7	1.7 - 2.3	>2.3
normalized ratio			
(INR)			

Child-Turcotte-Pugh Class obtained by adding score for each parameter (total points)

Class A = 5 - 6 points (mild liver disease)

Class B = 7 - 9 points (moderate liver disease)

Class C = 10 - 15 points (severe liver disease)

Table 6 Dose Modifications for Ibrutinib for Hepatic Impaired Subjects

Child-Pugh Class	Points	Dose Reduction for Ibrutinib
A	5 – 6	280 mg (two capsules)
В	7 – 9	140 mg (one capsule)
С	10 – 15	Hold Ibrutinib until resolved to moderate impairment (Child-Pugh class B) or better

Monitor subjects for signs of toxicity and follow dose modification guidance as needed.

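### Severe liver events fall under both Table 4 and Table 6 with no stated precedence: hold versus reduced-dose ibrutinib in Child-Pugh Class A or B, and different release criteria in Class C

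*Combined protocol and SAP*

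**What the plan says.** **Section 6.3.1 and Table 4.** The general rule reads: "Treatment with Ibrutinib should be held for any unmanageable, potentially study drug-related toxicity that is Grade 3 or higher in severity". The list of toxicities that lead to Table 4 ends with persistent gastrointestinal events, "or any other Grade 4 toxicity and any unmanageable Grade 3 toxicity". Liver events are not excluded. For a first occurrence Table 4 says "Hold Ibrutinib until recovery to Grade ≤ 1 or baseline; may restart" "at original dose level". A second occurrence restarts at 280 mg, a third at 140 mg, and a fourth ends ibrutinib. The text above the table adds "Ibrutinib may be held for a maximum of 28 consecutive days of toxicity" and requires discontinuation if toxicity above Grade 1 lasts longer than that.

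**Section 6.3.2 with Tables 5 and 6.** Subjects who develop significant liver dysfunction in the investigator's opinion, with transaminitis and jaundice as examples, "should be assessed with the Child-Pugh Score (Table 5) to determine a dose reduction of Ibrutinib as described in Table 6". Table 6 gives 280 mg for Class A (5–6 points) and 140 mg for Class B (7–9 points). Only Class C (10–15 points) is a hold: "Hold Ibrutinib until resolved to moderate impairment (Child-Pugh class B) or better". Table 6 states no recovery grade and no maximum hold. A closing line tells sites to monitor for toxicity and follow dose modification guidance as needed, without naming a table.

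**The concern.** A liver event can meet both triggers at once. A site that opens 6.3.1 holds ibrutinib; a site that opens 6.3.2 may continue it at a lower dose. This is a conflict between two written safety instructions about whether a subject with severe hepatotoxicity takes the drug.

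It also affects a listed result. Section 3.2.1 includes, as a Phase IB safety outcome, adverse events leading to discontinuation or dose delay. A hold would normally count as a delay, whereas a dose reduction is neither. The same event could therefore be counted or not, depending on the table used.

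The scenario is not remote. The protocol reports reversible Grade 4 AST and ALT increases in a healthy subject after a single 1,680 mg ibrutinib dose, which is above the study dose (6.3.3). It also reports one subject whose Grade 4 AST and Grade 3 ALT elevation led to discontinuation of obinutuzumab with fludarabine and cyclophosphamide (1.3.2.1, study GAO4779g).

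**Working it through.** The plan states no figure to reproduce here. The check scores the named liver examples with Table 5 and sets the two sets of instructions side by side.

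**Inputs (Table 5).** There are five measures: encephalopathy, ascites, bilirubin, albumin and INR. Each scores 1 to 3, so the total runs from 5 × 1 = 5 to 5 × 3 = 15. Class A is 5–6, B is 7–9 and C is 10–15. Transaminases are not among the measures.

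**1. Isolated transaminase rise.** With all five measures normal the score is 1 + 1 + 1 + 1 + 1 = 5, Class A, whatever the ALT or AST value. Table 6 gives 280 mg. If the event is Grade 4, or unmanageable Grade 3, Table 4 gives a hold. This example needs no grading threshold from outside the documents, because no enzyme value can change the score.

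**2. How far the no-hold rows reach.** With *k* measures at 3 points and the rest at 1, the score is 3*k* + (5 − *k*) = 5 + 2*k*:

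- *k* = 1: 7 points, Class B
- *k* = 2: 9 points, Class B
- *k* = 3: 11 points, Class C

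Two abnormal measures cannot exceed 9, so at least three of the five must be abnormal before Table 6 holds ibrutinib. Bilirubin above 3 mg/dL alone scores 3 + 4 × 1 = 7, Class B, 140 mg. I do not rely on the bilirubin case, because the documents do not reproduce the CTCAE liver thresholds and so do not show which grade that value carries.

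**3. The instructions side by side, for a liver event that meets the 6.3.1 trigger.**

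| | 6.3.1 / Table 4 | 6.3.2 / Table 6 |
|---|---|---|
| Class A | Hold | 280 mg, no hold |
| Class B | Hold | 140 mg, no hold |
| Class C | Hold | Hold |
| Release from hold | Grade 1 or lower, or baseline | Class B or better |
| Dose after a first event | Original level permitted | 140 mg (Class B) or 280 mg (Class A) |
| Maximum hold | 28 consecutive days | Not stated |

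**4. Release from a Class C hold.** Table 6 ends the hold at 9 points or fewer, when impairment may still be moderate. Table 4 requires Grade 1 or lower, or baseline. Section 6.3.2 says subjects with clinically significant Class B or C impairment at screening are excluded, so improvement to Class B is not in general a return to baseline. The documents give no mapping from class to grade that would make the two criteria equivalent.

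**5. Return to full dose.** The lowest possible score, 5, is still Class A. Table 6 therefore has no row that leads back to 420 mg, and it does not say when its reduction ends.

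**6. Precedence.** None is stated. By contrast, Table 7 refers recurrent Grade 3–4 events to Table 4 by number and restates the 28-day limit. Table 6 does neither.

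**The case against.** The strongest reply is that the two rules are cumulative. Section 6.3.2 opens by noting that ibrutinib is metabolised in the liver, and it uses the score to set a dose. On that reading, 6.3.1 governs toxicity: a Grade 4 event is held under Table 4, and Table 6 then sets the dose on resumption. The closing line after Table 6 keeps other guidance in force. Because Table 4 only says a first event may restart at the original level, restarting lower satisfies both tables.

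Much of this stands. The reading is coherent, and it softens the restart-dose difference: the tables permit different doses after a first event, but one course can comply with both. Two things remain. The documents do not state this reading or the order of the two tables, and it leaves the two release criteria unreconciled.

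Section 7 also lets the principal investigator remove a subject whenever that is medically prudent. This is a real safeguard for the individual, but it does not settle what the text instructs.

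Four stronger inferences are tempting, and the documents do not support them:

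- **That the tables always oppose each other.** In Class C both hold; only the release point differs.
- **That they set different hold limits.** The 28-day limit is general text in 6.3.1 and Table 6 is silent, so the limit may cover both. It cannot simply be assumed to, because section 6.2.12 allows an ibrutinib delay of up to 8 weeks for tumor lysis syndrome.
- **That every Grade 3 liver event is caught.** The 6.3.1 list covers unmanageable Grade 3 only, although the Table 4 column header refers to Grade 3 or higher.
- **That the response rate or power suffers.** Nothing shows that a hold or a reduction costs a response, and section 3.2.2 counts responses over the course of the study.

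**Conclusion.** The point holds in a bounded form. For a liver event that is Grade 4 or unmanageable Grade 3 and scores 5 to 9 points, Table 4 says hold and Table 6 gives a reduced dose without a hold. The isolated Grade 4 transaminase rise shows this from the documents alone. For 10 to 15 points the action agrees, but the release criteria differ. After a first event Table 4 permits the original dose and Table 6 offers no row back to 420 mg. Precedence and the reach of the 28-day limit are unstated.

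The conclusion assumes that the 6.3.1 trigger includes liver events, since nothing excludes them, and that the closing line after Table 6 does not itself set an order. The documents give no incidence of such events for this combination, so the size is stated as the range of scores and grades affected, not as a number of subjects. The weight rests on safety and on consistent recording of holds and reductions, not on the efficacy design.

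**What to change.** The sponsor should reconcile 6.3.1/Table 4 with 6.3.2/Table 6 by stating:

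1. which rule governs when a liver event meets the 6.3.1 trigger, or that both apply and in what order;
2. one consistent recovery criterion and restart rule for these events, including whether and when a subject may leave the Table 6 dose;
3. whether the 28-day limit applies to Table 6 holds.

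An explicit cross-reference of the kind already used in Table 7 would do. Which rule is clinically right is for the sponsor to decide. The cost is a few sentences in two adjacent subsections at the next amendment, with no added procedures or subjects.

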6.3.3 Ibrutinib Overdose

Any dose of study drug in excess of that specified in this protocol is considered to be an overdose. Signs and symptoms of an overdose that meet any Serious Adverse Event criterion must be reported as a Serious Adverse Event in the appropriate time frame and documented as clinical sequelae to an overdose.

There is no specific experience in the management of ibrutinib overdose in subjects. No maximum tolerated dose (MTD) was reached in the Phase 1 study in which subjects received up to 12.5 mg/kg/day (1400 mg/day). Healthy subjects were exposed to up to single dose of 1,680 mg. One healthy subject experienced reversible Grade 4 hepatic enzyme increases (AST and ALT) after a dose of 1,680 mg. Subjects who ingested more than the recommended dosage should be closely monitored and given appropriate supportive treatment. Refer to Section 11.4.3.8 for further information regarding special reporting situations as a result of overdose

Ibrutinib + GA101 - Obinutuzumab. University of California, San Diego

Dose Modifications and delays for GA101 – Obinutuzumab

Splitting the first dose of GA101 – Obinutuzumab in Cycle 1 is mandatory. The first dose (1,000 mg) must be administered over Days 1 and 2 (100 mg on Day 1 and 900 mg on Day 2). Infusions should be interrupted or slowed if subjects experience infusion reactions (see Section 6.2.11). If a planned dose of GA101 - Obinutuzumab is missed, it should be administered as soon as possible and the next cycle should begin 28 days later. Do not wait until the next planned dose.

No reduction in the dose of GA101 - Obinutuzumab is allowed. A dose delay of up to 8 weeks is permitted for GA101 - Obinutuzumab to allow recovery of hematologic toxicities to \leq Grade 2 or non-hematologic toxicities to Grade 1 or baseline level. If the treatment is delayed for more than 8 weeks because there is no improvement of cytopenia to \leq Grade 2, treatment under this protocol will be discontinued and the subject will continue in follow-up until the beginning of new treatment or death.

If a subject experiences grade 3 or 4 cytopenia, the guidelines for GA101 – Obinutuzumab and Ibrutinib dose-delay are outlined in Table 7:

Table 7 Dose Modification for Cytopenias

Grade	GA101 - Obinutuzumab	Ibrutinib
Grade 3 or 4 cytopenia ^{a, c}	Delay dose for a maximum of 8 weeks. If improvement to ≤ Grade 2 ^b , administer full dose. If delay more than 8 weeks because there is no improvement of cytopenia < Grade 3, subject will be withdrawn from the study treatment but will continue in follow-up until the beginning of new treatment or death.	Hold Ibrutinib until recovery to Grade ≤ 1 ^b ; restart Ibrutinib at 420 mg daily. For subjects with recurrent episodes of grade 3 - 4 AEs a dose modification action is described in table 4 (see section 6.3.1). Ibrutinib may be held for a maximum of 28 consecutive days of toxicity. Ibrutinib should be discontinued in the event of a toxicity lasting > 28 days and the subject will be withdrawn from the study treatment but will continue in follow-up until the beginning of new treatment, death or assessment of TFS and OS.

Ibrutinib + GA101 – Obinutuzumab. University of California, San Diego

Grade 1 or 2 cytopenia ^{a, c}	No dose reduction or delay	No dose reduction.
--	----------------------------	--------------------

- a In subjects with cytopenia at baseline, dose modifications will be based on the IWCLL Guidelines for hematological toxicity in CLL studies (Hallek et al., 2008). For subjects with a normal neutrophil count, platelet count, and/or hemoglobin value at baseline, the NCI-CTCAE v4.0 grading system will be used.
 - b Or baseline.

° Subjects with cytopenia at baseline should have hemoglobin ≥ 8 g/dL, platelets count ≥ 40 x10³/mm³ and absolute neutrophil count (ANC) ≥ 1.0×10^9 cells/L in order to proceed with the study treatment. Transfusion and Growth factors will be permitted and must be documented in the medical chart.

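### Section 6.3.1 and Table 7 set different ibrutinib hold triggers for cytopenia, and no text says which prevails or which episodes count towards Table 4

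*Combined protocol and SAP*

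**What the plan says.** Section 6.3.1, on ibrutinib holds, reductions and discontinuation, opens with a general rule: "Treatment with Ibrutinib should be held for any unmanageable, potentially study drug-related toxicity that is Grade 3 or higher in severity". It then says "The actions in Table 4 should be taken for the following toxicities" and lists them:

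- for neutrophils, "Grade 4 ANC (< 500/μL) for > 7 days";
- Grade 3 or 4 platelets below 50,000/µL or, in subjects with baseline thrombocytopenia, "a platelet decrease of 50-74% from baseline in presence of bleeding";
- Grade 4 platelets, with a separate definition for baseline thrombocytopenia;
- persistent Grade 3 or 4 gastrointestinal toxicity, or "any other Grade 4 toxicity and any unmanageable Grade 3 toxicity".

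Table 7 stands under the heading on obinutuzumab modifications and delays (cited in 10.2.5 as Section 6.3.4), but has a column for each drug. For any Grade 3 or 4 cytopenia the ibrutinib column reads "Hold Ibrutinib until recovery to Grade" 1 or lower, or baseline by its footnote, with restart at 420 mg. Recurrent episodes are sent to Table 4.

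The 28-day sentences also differ. Section 6.3.1: "Ibrutinib should be discontinued in the event of a toxicity > Grade 1 lasting > 28 days". Table 7: "Ibrutinib should be discontinued in the event of a toxicity lasting > 28 days", followed by withdrawal of the subject from study treatment.

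Section 10.2.5 points to Table 4 for ibrutinib and to Table 7 for Grade 3 or 4 cytopenia. It does not say what to do where they disagree.

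**The concern.** Both passages are operative and both speak directly to neutrophils and platelets. For some cytopenias one calls for a hold and the other lists no action, so the same event can be managed differently depending on the page consulted.

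Three things are at stake. First, consistent handling of a toxicity that the protocol itself describes as frequent. Second, adverse events leading to discontinuation or dose delay are a listed Phase IB safety outcome (Section 3.2.1), and that outcome partly records which rule was applied. Third, Table 4 steps the dose down with each further occurrence and stops ibrutinib at the fourth, so whether an episode counts matters beyond the episode itself. Ibrutinib continues for 3 years after cycle 6, and blood counts on Days 1, 8, 15 and 22 of the treatment cycles (Section 9.2) make short episodes likely to be seen.

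**Working it through.** The point rests on no sample size, power or error rate, and the plan states no figure to reproduce. The check is a side-by-side reading of 6.3.1/Table 4 and Table 7, using the grading in Appendix 3.

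**Hold triggers**

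| Event | Section 6.3.1 | Table 7 |
|---|---|---|
| Grade 3 neutropenia, manageable | Not listed: the neutrophil trigger needs Grade 4, and the residual category needs an unmanageable event | Hold |
| Grade 4 neutropenia, 7 days or less, manageable | Not listed: the trigger needs more than 7 days, and the Grade 4 residual category covers other toxicities | Hold |
| Grade 3 anemia, manageable | Not listed: falls to the residual category, which needs an unmanageable event | Hold |
| 50-74% platelet fall, baseline thrombocytopenia, no bleeding | Not listed: the trigger needs bleeding | Hold (Grade 3 in Appendix 3) |
| Platelets below 50,000/µL, no baseline thrombocytopenia, no bleeding, not Grade 4 | Unclear whether the bleeding condition also governs this clause | Hold |
| Grade 4 neutropenia, more than 7 days | Act | Hold |
| Grade 4 platelets | Act | Hold |
| Grade 4 anemia | Act (other Grade 4) | Hold |

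The first four rows diverge, the fifth depends on how the platelet sentence is parsed, and the last three agree.

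**Counting for Table 4.** Take four separate episodes of brief, manageable Grade 3 neutropenia. Through Table 7, recurrences go to Table 4: restart at the original dose, then 280 mg, then 140 mg, then discontinuation. Through the list in 6.3.1, none of the four qualifies. Table 4's own column heading counts adverse events of Grade 3 or above, which is wider than the list that leads into it, so the table does not settle the question.

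**28-day condition**

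- Read literally, residual Grade 1 cytopenia beyond 28 days meets Table 7's sentence but not that of 6.3.1.
- The reverse can occur for neutrophils. Eligibility admits an ANC from 1.0 × 10⁹/L, and 1000 to below 1500/µL is Grade 2 in Appendix 3. A subject back at such a baseline may restart under Tables 4 and 7, yet can meet the discontinuation sentence of 6.3.1. Platelets and hemoglobin are graded in Appendix 3 by percentage fall from the pretreatment value, so this variant does not arise for them on that scale.
- The stated consequence differs: ibrutinib stopped (6.3.1), or the subject withdrawn from study treatment (Table 7).

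**Points of agreement.** Both passages give a maximum hold of 28 consecutive days, recovery to Grade 1 or lower or baseline, and the original 420 mg after a first episode.

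**How common.** Section 1.2.4.9 reports Grade 3 or 4 cytopenia in 41% of subjects on ibrutinib, with neutropenia in 29%. Applied to the planned 32 subjects:

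- neutropenia: 0.29 × 32 = 9.28, about 9;
- any cytopenia: 0.41 × 32 = 13.12, about 13.

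These count every Grade 3-4 cytopenia, including the rows on which the passages agree. The protocol gives no split by grade, duration, bleeding or manageability, so the number in the divergent rows cannot be derived.

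**The case against.** The strongest reply is that the protocol already routes the reader. The sentence introducing Table 7 sends Grade 3 or 4 cytopenia there for both drugs, 10.2.5 repeats this, and Table 7 sends recurrences on to Table 4. On that reading the specific rule displaces the general one. Nor does 6.3.1 forbid a hold in cytopenias outside its list, so a site that always follows Table 7 breaches no sentence of 6.3.1.

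Part of this stands: 6.3.1 is silent on the divergent events rather than requiring that ibrutinib continue, and a workable reading exists. It does not remove the problem. Section 6.3.1 is itself specific on neutrophils and platelets, and if Table 7 governs every Grade 3 or 4 cytopenia, the duration and bleeding conditions in 6.3.1 have no function. It also leaves open which episodes count for Table 4.

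The reply is stronger on the 28-day sentences. Read with its own cell, Table 7's unqualified toxicity most naturally means one that has not recovered to Grade 1 or baseline, which is close to 6.3.1. What remains is the subject whose baseline is above Grade 1, and the differing consequence.

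A reader might also infer that restart grades conflict. They do not. Nor do the documents support saying that 6.3.1 requires bleeding for every Grade 3 platelet event: the condition is written next to the baseline-thrombocytopenia clause and may belong to that clause alone.

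**Conclusion.** The two passages give different ibrutinib hold triggers for four identifiable kinds of cytopenia, and the protocol does not say which prevails. The count of Table 4 occurrences inherits the ambiguity. The 28-day wording is a secondary and narrower difference.

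The neutropenia and anemia divergences do not depend on the ambiguous platelet sentence. They assume the events are manageable, since an unmanageable, potentially drug-related event of Grade 3 or higher is held under 6.3.1 as well.

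Three stronger readings are not supported:

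- That 9 to 13 of 32 subjects would be treated differently. That is at most a ceiling, and it assumes that the ibrutinib rates carry over to this combination, which the documents do not establish.
- That the 5 of 6 subjects with Grade 3-4 neutropenia in the cited run-in show what obinutuzumab adds. Those subjects also received chlorambucil, which Section 1.4 says may increase cytopenias.
- That response is affected. Nothing in the documents links the holds in question to response. The listed outcome that is touched is a Phase IB safety outcome, and that phase comprises 6 subjects.

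The inconsistency should be corrected. It does not undermine the efficacy design.

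**What to change.** Reconcile Section 6.3.1/Table 4 with Table 7, and carry the result into the cross-reference in 10.2.5, so that for ibrutinib in cytopenia the protocol states:

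- one set of hold triggers, including whether the bleeding condition applies to the 50,000/µL platelet criterion;
- one 28-day discontinuation condition, with its grade threshold, its application to a subject whose baseline is above Grade 1, and its consequence (ibrutinib stopped, or withdrawal from study treatment);
- which episodes count as occurrences for Table 4.

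Restart grades need no change. Which triggers and which discontinuation condition apply is a clinical decision for the sponsor, and this review takes no position on it. The cost is amendment wording; sample size and analysis are unaffected.

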Following oral administration of Ibrutinib at doses ranging from 1.25 to 12.5 mg/kg/day as well as fixed dose levels of 420, 560, and 840 mg/day, exposure to Ibrutinib increased as doses increased with substantial intersubject variability. The mean half-life ($t_{1/2}$) of Ibrutinib across 3 clinical studies ranged from 4 to 9 hours, with a median time to maximum plasma concentration (T_{max}) of 2 hours. Administration of 420 mg Ibrutinib with a high-fat breakfast in subjects with CLL approximately doubled the mean systemic exposure compared to intake after overnight fasting with median time to T_{max} delayed from 2 to 4 hours. Ibrutinib is metabolized by hepatic cytochrome P450 (CYP) 3A enzymes and to a minor extent by CYP2D6. Metabolism is the major route of elimination. Ibrutinib is metabolized to the dihydrodiol metabolite PCI-45227, a reversible inhibitor of BTK, with approximately 15 times lower inhibitory potency compared to Ibrutinib. The metabolite-to-parent AUC ratio ranged from 0.7 to 3.4. Steady-state exposure of Ibrutinib and PCI-45227 was less than 2-fold of first dose exposure.

The results of human mass balance study of [14C]-Ibrutinib conducted in six healthy male subjects demonstrated that less than 10% of the total dose of [14C]-Ibrutinib is renally excreted, whereas approximately 80% is recovered in feces. Subjects with mild and moderate renal insufficiency (creatinine clearance > 30 mL/min) were eligible to enroll in Study PCYC-1102-CA in which pharmacokinetic (PK) assessments were included. No dose adjustment is needed for mild or moderate renal impairment (greater than 30 mL/min creatinine clearance). There is no data in subjects with severe renal impairment or subjects on dialysis. The study of ibrutinib in hepatic impaired subjects is currently in progress.

1.2.3 Clinical Experience with Ibrutinib

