6.4.2 Medications to be used with Caution

6.4.2.1 CYP3A- Inhibitors/Inducers

Ibrutinib is metabolized primarily by CYP3A4. Concomitant use of ibrutinib and drugs that strongly or moderately inhibit CYP3A can increase ibrutinib exposure and therefore strong CYP3A inhibitors should be avoided.

- If a strong CYP3A inhibitor (eg, ketoconazole, indinavir, nelfinavir, ritonavir, saquinavir, clarithromycin, telithromycin, itraconazole, nefazodone, cobicistat, and posaconazole) must be used, reduce ibrutinib to 140 mg for the duration of the inhibitor use or withhold ibrutinib treatment temporarily (for 7 days or less). Subjects should be monitored for signs of ibrutinib toxicity.
- If a moderate CYP3A inhibitor (eg, fluconazole, voriconazole, erythromycin, amprenavir, aprepitant, atazanavir, ciprofloxacin, crizotinib, diltiazem, fosamprenavir, imatinib, verapamil, amiodarone, and dronedarone) is indicated, reduce ibrutinib dose to 140 mg for the duration of the inhibitor use.
- No dose adjustment is required in combination with mild inhibitors.
- Avoid grapefruit and Seville oranges during ibrutinib treatment as these contain moderate inhibitors of CYP3A (see Section 6.1.2).

Avoid concomitant use of systemic strong CYP3A inducers (eg, carbamazepine, rifampin, phenytoin, and St. John's Wort). Consider alternative agents with less CYP3A induction.

A list of common CYP3A inhibitors and inducers is provided in appendix 5. For further information, please refer to the current version of the IB and examples of inhibitors, inducers, and substrates can be found at http://medicine.iupui.edu/clinpharm/ddis/maintable/. This website is continually revised and should be checked frequently for updates.

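### Table 7 restarts ibrutinib at a fixed 420 mg after a first Grade 3-4 cytopenia, with no exception for a subject whose dose is limited by Table 6 for liver dysfunction

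*Combined protocol and SAP*

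**What the plan says.** Table 7 (Section 6.3.4) covers Grade 3 or 4 cytopenia. Ibrutinib is held until the count recovers to Grade 1 or to baseline, and the instruction is then to "restart Ibrutinib at 420 mg daily". Recurrent episodes are sent to Table 4 (Section 6.3.1), so the 420 mg figure governs the first episode. Table 4 gives 280 mg after a second event, 140 mg after a third, and discontinuation after a fourth.

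Section 6.3.2 sets a separate limit. A subject who, in the investigator's opinion, develops significant liver dysfunction on study is scored by Table 5. Table 6 then gives 280 mg for Child-Pugh class A, 140 mg for class B and a hold for class C. The line below Table 6 reads "Monitor subjects for signs of toxicity and follow dose modification guidance as needed".

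Section 6.4.2.1 limits the dose for drug interactions. With a moderate CYP3A inhibitor the instruction is to "reduce ibrutinib dose to 140 mg for the duration of the inhibitor use". A strong inhibitor that must be used carries the same 140 mg dose for the same period, or a short hold.

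**The concern.** Table 7 states an absolute dose in milligrams, while Table 6 may be holding the same subject at a lower one. Staff working from Table 7 could raise the dose above the hepatic limit in someone who has just recovered from a Grade 3-4 cytopenia.

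The protocol gives reasons for care here. Section 6.3.2 explains the entry exclusion with the words "Ibrutinib is metabolized in the liver and therefore subjects with clinically significant hepatic impairment", and Section 1.2.2 adds "The study of ibrutinib in hepatic impaired subjects is currently in progress". How far exposure changes with hepatic impairment is not quantified.

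There is also a reporting consequence. Section 6.3.3 states "Any dose of study drug in excess of that specified in this protocol is considered to be an overdose", and Section 11.4.3.8 lists overdose among the situations to be recorded in the CRF. The same 420 mg restart would comply with Table 7, yet count as an overdose if Table 6 governs.

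**Working it through.** The plan has no statistical figure to reproduce on this point. The check is a comparison of the dosing rules, followed by dose ratios.

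**Inputs**
- Table 7, first Grade 3-4 cytopenia: 420 mg.
- Table 6: 280 mg (class A), 140 mg (class B), hold (class C).
- Table 4: 280 mg (second event), 140 mg (third event).
- Section 6.4.2.1: 140 mg with a moderate inhibitor, or a strong one that must be used.
- Table 5: five measures, each scored 1 to 3; class A is 5-6 points.

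**Step 1. Who falls under Table 6?** The lowest possible total is 5 × 1 = 5, which is already class A. Every subject who is scored therefore receives at least the 280 mg limit. Exclusion criterion 18 (Section 4.2) removes only classes B and C, and only at entry, so it does not prevent liver dysfunction arising later.

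**Step 2. Does Table 7 give way?** Its three footnotes deal with the grading scale, baseline as an alternative recovery target, and blood-count thresholds. None touches the restart dose. The sentence introducing Table 7, and Section 10.2.5, describe it as guidance on delaying doses; neither mentions Table 6 or Section 6.4.2.1.

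**Step 3. Does Table 6 keep its limit in force?** It links the dose to the Child-Pugh class, but says neither how long a reduction lasts nor that it survives a hold for another reason. The line beneath it points staff to other dose guidance, and Table 7 is such guidance. Nothing settles the order of precedence.

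**Step 4. Does Section 6.4.2.1 keep its limit in force?** Yes. Its 140 mg lasts as long as the inhibitor is taken, and nothing in Table 7 ends that period.

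**Step 5. Ratio of the literal dose to the hepatic limit**

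| Rule read literally | Limit in force | Ratio |
|---|---|---|
| Table 7, first cytopenia, 420 mg | Class A, 280 mg | 420 / 280 = 1.5 |
| Table 7, first cytopenia, 420 mg | Class B, 140 mg | 420 / 140 = 3.0 |
| Table 4, second event, 280 mg | Class A, 280 mg | 280 / 280 = 1.0 |
| Table 4, second event, 280 mg | Class B, 140 mg | 280 / 140 = 2.0 |
| Table 4, third event, 140 mg | Class B, 140 mg | 140 / 140 = 1.0 |

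The excess therefore arises in Table 7 for both classes, and in Table 4 at the second event for a subject limited to 140 mg. In that last case a row meant as a step down would double the dose.

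**The case against.** The best defence is that Table 7 describes the ordinary case. Every subject is assigned 420 mg, and the table is introduced as guidance on delays. Its message may be only that a first cytopenia, taken alone, calls for no lasting reduction. Limits set for different reasons can all be obeyed by giving the lowest dose. Table 6 appears to follow current status, since its class C row keeps the drug on hold until class B or better, and recovery of blood counts does not change hepatic class. The line under Table 6 is most naturally read as calling for further reductions, not as permission to raise the dose. The study has one centre, so sites cannot diverge, and the entry criteria narrow the overlap.

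Most of this stands as a description of what a careful clinician would probably do. It makes the point a gap in the wording of a dosing rule, with a limited chance of error. It does not close the gap. Table 7 is an instruction with a milligram figure, and the reader has to infer that another table caps it. Nor does this defence remove the 280 mg figure in Table 4.

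A reader might infer that CYP3A inhibitors create an equal conflict. The text does not support that, for the reason in step 4. In addition, Section 6.1.2 says CYP3A inhibitors should be avoided, and criterion 17 excludes subjects who need continuous treatment with a strong one.

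**Conclusion.** The point holds for the hepatic limit. Read literally, Table 7 gives 1.5 times the class A dose and 3 times the class B dose, and Table 4 gives twice a 140 mg limit at the second event. These are ratios of doses. A reader might take them as measures of exposure or harm, but the documents give no exposure data for hepatic impairment. A reader might also call a 420 mg restart a definite overdose; it is one only if Table 6 prevails, and that is the question left open.

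The number of subjects affected cannot be derived. It is tempting to apply the 41% rate of Grade 3-4 cytopenia in Section 1.2.4.9 to 32 subjects: 0.41 × 32 = 13.1. Assumed shares of 5%, 10% and 20% with a limit in force, independent of cytopenia, would then give 0.66, 1.31 and 2.62 subjects. The documents do not support this as an estimate. That section does not define the population, regimen or grading scale behind the 41%, and the shares have no source. The calculation also ignores that the episode must be the first, must resolve within the 28 days allowed for a hold, and must end with the limit still applying. The number is probably small.

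The dosing rule does not enter the Simon design (10 then 22 subjects, null 78%, alternative 94%) or the ORR analysis, and both are unaffected. The correction is worth making because it protects subjects at almost no cost.

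**What to change.** In Table 7, replace "restart Ibrutinib at 420 mg daily" with: *restart Ibrutinib at 420 mg daily or, if a lower limit under Table 6 or Section 6.4.2.1 applies at the time of restart, at that limit*. This also supplies the cross-reference needed for CYP3A inhibitors. The time of restart is the right reference point. Tying the restart to the dose taken before the hold would keep a subject at 140 mg even if the inhibitor had been stopped during the hold.

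Add a footnote to Table 4 stating that its milligram doses are subject to the same cap.

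The cost is one clause and one footnote at the next amendment, with no added visits, procedures or subjects.
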